## **Participants, inclusions- and exclusions criteria**

There are 24-48 children on each of the DCSH. They have a continuously admission of children in the age range 7-14 years, and every child is offered a 10 weeks residential stay. From september 2018 about 600 children (boys and girls) will be recruited from two DCSH.

Inclusions criteria:

- Boys and girls in a 10-week residential stay at the DCSH in the age of 7-14 year.
- Informed consent from parents/legal guardian.
- Willingness to participate in training and tests.

Exclusions criteria:

- Participants, of which the scientists do not find, suited to follow the procedures of the protocol and the program for training and testing.

Participants can at all times choose to withdraw from tests, if this is desired or necessary due to illness or injury. All children at the DCSH participate in the training as part of the scheduled program.

The specific reasons to include individuals, who cannot give informed consent, are group C, cf. Comity law §19: “That the project can only be completed by including individuals, whom are in the specific age

group, illness or condition, and that the project have a direct possibility to transfer large positive advantages to the patient population that consist of the same age group, illness or condition as the participant, and that the project involve minimal risk and inconvenience for the child or the young participant". The project can give valuable information on health-related training effects and form the foundation for physical activity recommendations for overweight children in Denmark. The project is also useful for any specific participant, as participants and parents, besides for the training, achieve knowledge about physical capacity and health. Furthermore, there are minimal risks for the participant in relation to the tests, measurements and training.

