### Statistic and power calculation

The primary outcome of the project is fat percentage, and among the most important secondary outcomes are aerobic fitness, health-knowledge and well-being. The power calculation is based on the result of the pilot project (Ørntoft et al. 2016). The power calculation is measured with t-test. Some variables are expressed in table below and are based on the development on variables from the pilot study and a study with children from the same age group as on the DCSH (Bendiksen et al. 2014). The calculations are based on a power of 0.80 and p-value of 0.05.

Calculation of number of participants (N) in relation to the evaluation on the DCSH standard program and the assessment of activity and health-program (HIHE).

Power calculation	Intervention group (HIHE)	Standard group	IG vs SG	Delta IG SG Sample size
Fat percentage, intervention period	-9.6 (4.2)	-8.9 (3.7)	-0.6 (2.3)	232
Fat percentage, follow- up period	5.0 (13.4)	8.4 (12.9)	-3.3 (11.2)	182
Aerobic fitness	148 (63)	-106 (83)	254 (85)	4
Health-knowledge	11.9 (23.5)	2.6 (23.7)	9.4 (23.5)	100
Muscle mass	0.6 (0.7)	0.5 (0.9)	0.6 (0.8)	29

Number of participants, 1:1 randomisation	Number of participants with 75% at post-tests
464	580
364	455
8	10
200	250
58	73

The calculations are based upon a randomisation of 1:1, 50% of the participants participate in the standard program. Based on the power calculation, the total number of participants is estimated to be approx. 600 children. This is under the consideration of a completion rate of 75%.

All outcomes will be analyzed by means of linear mixed models including two-way interaction between intervention (standard and intervention) and time (before and after) as fixed effect and child and site as random effects (to account for differences between children and between sites, respectively). Adjustment for age, sex, and possibly other covariates/confounders will also be included as fixed effects in the models.

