## Method

### Design

Approximately 600 boys and girls in the age 7-14 years are recruited from two DCSH. The design is a cross-over design at DCSH level over a two-year period with two intervention groups: A standard group (with the standard program (SG)) and a standard + HIHE (SG+). In SG+ the children will, in addition to the standard program, play recreational football 2x45 min. a week. In SG the children will perform the planned activities according to the schedule. The training in SG+ will be performed indoor or outdoor on grass (depending on the facilities on the specific DCSH) with different football exercises (dribbling, ball control, passes etc.) and small-sided games with high intensity (3v3 to 5v5) on two goals. All training sessions take place on the DCSH or in the immediate vicinity of the DCSH. Every week, a specific football skill is connected with a health message. E.g., the skill of passing the ball to each other is related to respect of each other and avoid bullying.

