### **Recruitment of participants**

The participants are recruited from two DCSH. In the project's cooperation agreement, it is specified that two of the DCSH change practice for one year. In this manner, all the children at the two DCSH are participating in the HIHE intervention, regardless of their participation in tests. To investigate the standard program, all tests will be carried out at both of the DCSH for one year. After the first year the two participating DCSH change intervention group. Alongside the general information about the stay at the DCSH, written information about the study will be provided and subsequently an oral information meeting / parent meeting cf. the description below.

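### With only two houses, a random site effect adjusts level but not change; site and site x time should be fixed effects, and the stay's change shown for each house

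*Combined protocol and SAP*

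**What the plan says.** The section on statistics and power calculation plans linear mixed models for all outcomes. The fixed part is the "two-way interaction between intervention (standard and intervention) and time (before and after) as fixed effect". The random part of the model is "child and site as random effects", and the stated purpose is to allow for children and houses that differ from one another. On covariates the section says: "Adjustment for age, sex, and possibly other covariates/confounders will also be included as fixed effects in the models". No random slope, site x time term or year term is named, so I read the site term as a random intercept.

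The number of houses is two. The design section states: "Approximately 600 boys and girls in the age 7-14 years are recruited from two DCSH". The participants section agrees: "about 600 children (boys and girls) will be recruited from two DCSH".

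Each house supplies children to both programmes. The design section says: "The design is a cross-over design at DCSH level over a two-year period with two intervention groups". The recruitment section says: "After the first year the two participating DCSH change intervention group".

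The hypothesis section also makes a claim about the 10-week stay itself, worded for the Danish Christmas Seal Houses (DCSH) in general.

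**The concern.** The site term is meant to account for differences between houses, but it does not do so for the quantity under test. With two levels its variance is barely estimable. As an intercept it describes only how far apart the houses lie in level, and level drops out of a before-after change. No named term lets the change differ by house.

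Two results are affected. The first is the HIHE estimate: the arms are filled in different years, so the mix of houses can differ between arms, and a house with the larger fat loss would then count for more in one arm than in the other. The second is the effect of the stay: it is a before-after change pooled over two houses, and its standard error reflects variation between children only.

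**Working it through.** **Inputs from the statistics and power section.** Planned difference in fat percentage over the intervention period 0.6, SD 2.3, 232 per arm, power 0.80, alpha 0.05; SD of change in the standard group 3.7. **Assumed, because the documents give no figure:** a 1-point house difference in fat-percentage change, intraclass correlations (ICC) between 0 and 0.10, and a between-house SD in change of 0.5.

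**1. The plan's own figure.** n per arm = 2 x (1.960 + 0.842)^2 x 2.3^2 / 0.6^2 = 230.7, so 231. The t-test version gives 231.6, so 232. The plan's figure reproduces with a two-sided test.

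**2. Information on the site variance.** Degrees of freedom = 2 - 1 = 1. A 95% interval for such a variance runs from about 0.2 to 1018 times the estimate. With m = 232 children per house, the chance of a zero estimate is P(F(1, 462) < 1/(1 + m x ICC/(1 - ICC))):

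| ICC | Chance of a zero estimate |
|---|---|
| 0 | 68% |
| 0.01 | 42% |
| 0.05 | 22% |
| 0.10 | 15% |

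**3. Effect of the site variance on the HIHE contrast.** The planned model was fitted to simulated data with the site variance set at values from 0 to 1000. With complete before and after data, the intervention x time estimate and its standard error (0.2135) were identical throughout. With 25% of post-tests missing, the estimate moved by less than 0.003. The term therefore adjusts almost nothing in the tested contrast, whatever its estimated size.

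**4. Leakage of a house difference in change.** Bias = (share of house A in the HIHE arm - share of house A in the standard arm) x house difference in change. The planned model, fitted to noise-free data with a true HIHE effect of -0.6 and house A losing 1 point more, gave:

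| Children, house A (HIHE / standard) | Children, house B (HIHE / standard) | Share of A (HIHE vs standard) | Bias |
|---|---|---|---|
| 116 / 116 | 116 / 116 | 50% vs 50% | 0.00 |
| 77 / 77 | 155 / 155 | 33% vs 33% | 0.00 |
| 130 / 102 | 102 / 130 | 56% vs 44% | -0.12 |
| 139 / 93 | 93 / 139 | 60% vs 40% | -0.20 |

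The last row is 0.20/0.6 = one third of the planned effect. With site and site x time fixed, the estimate was -0.60 in every layout.

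**5. What a bias of 0.2 would do.** The standard error at 232 per arm is 2.3 x sqrt(2/232) = 0.2135, and 0.2/0.2135 = 0.94. If HIHE has no effect, the chance of a significant result is P(Z > 1.96 - 0.94) + P(Z < -1.96 - 0.94), about 15% instead of 5%. If the bias runs against HIHE, the apparent effect is 0.4 and power is P(Z > 1.96 - 0.4/0.2135), about 47% instead of 80%.

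**6. The effect of the stay.** The model standard error in the standard arm is 3.7/sqrt(232) = 0.24. With a between-house SD in change of 0.5 it would be sqrt(0.24^2 + 0.5^2/2) = 0.43. The pooled figure also depends on house sizes: with house changes of -9.9 and -8.9 it is -9.40 for equal houses and -9.23 when the second house is twice as large.

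**7. Precision after the change.** The standard error of the HIHE effect with site x time fixed is 2.3 x sqrt(1/sum of n1 x n0/(n1 + n0) over houses). It is 0.2135 with equal shares, as before, and 0.2179 with shares of 60% against 40%.

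**The case against.** The strongest reply is that the design already protects the HIHE comparison. Each house is its own control, so a stable house difference in change cancels when the shares are equal, even if one house is twice the size of the other. That stands. A reader might infer that house differences in change are always left in the HIHE estimate; the documents do not support this.

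Unequal shares are also an assumption. The plan gives no split by year and aims at 1:1. The recruitment section does not settle whether the houses run the programmes in opposite order. If they do, a common 40:60 split of intake between years gives shares of 40% against 60%; opposite splits in the two houses would cancel. If both houses run HIHE in the same year, a common split gives equal shares, and leakage needs the houses' relative intake to change between years. All this stands as a limit on the size of the problem. On the other side, admission is continuous, the arms are separated by year, non-completion of 25% is allowed for, and nothing in the plan holds the shares equal.

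A reader might also infer that a site variance estimated as zero damages the primary comparison. It does not (step 3). When the houses do not differ, zero is the right answer, and for larger house differences a zero estimate is not frequent.

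Finally, a reader might take the random label as a claim about all houses, or demand an interval for the stay based on t with 1 degree of freedom. The plan gives the purpose of the term as accounting for differences between sites, and such an interval would only illustrate how little two houses say about others. A fixed-effect model's interval would likewise reflect children only, so for the stay the remedy lies in reporting and wording.

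**Conclusion.** The point holds as an inexpensive improvement, not as a demonstrated bias. It is certain from the text that there are two houses and that the plan names no term for house differences in change. Given the random-intercept reading, the site term has 1 degree of freedom for its variance and cancels from the tested contrast.

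The size of any bias in the HIHE estimate is conditional: zero with equal house shares, 0.12 per point of house difference at 56% against 44%, and 0.20 at 60% against 40%. The 1-point difference and the unequal shares are assumptions.

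The point about the stay needs no imbalance. Its standard error leaves out between-house variation in change, and so cannot support a statement about DCSH in general. The increase from 0.24 to 0.43 depends on the assumed between-house SD of 0.5.

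**What to change.** In the model paragraph of the statistics and power section, replace the random site effect by site and site x time as fixed effects, and keep child as a random effect. HIHE is then compared within house. Report the change over the stay for each house beside the pooled figure, and limit the conclusion on the first aim to these two houses.

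The cost is one sentence in the plan and one or two degrees of freedom. The standard error of the HIHE effect stays at 0.2135 with equal shares and is 0.2179 at 60% against 40%, about 2% more (0.2179/0.2135 = 1.02). The 232 per arm, recruitment and measurements need no change. What is given up is a formal claim about houses not studied, which two houses could not support anyway.

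This change does not remove house-by-year variation or calendar-year confounding; those need to be dealt with separately.

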## Method

### Design

Approximately 600 boys and girls in the age 7-14 years are recruited from two DCSH. The design is a cross-over design at DCSH level over a two-year period with two intervention groups: A standard group (with the standard program (SG)) and a standard + HIHE (SG+). In SG+ the children will, in addition to the standard program, play recreational football 2x45 min. a week. In SG the children will perform the planned activities according to the schedule. The training in SG+ will be performed indoor or outdoor on grass (depending on the facilities on the specific DCSH) with different football exercises (dribbling, ball control, passes etc.) and small-sided games with high intensity (3v3 to 5v5) on two goals. All training sessions take place on the DCSH or in the immediate vicinity of the DCSH. Every week, a specific football skill is connected with a health message. E.g., the skill of passing the ball to each other is related to respect of each other and avoid bullying.

### Training protocol

#### Recreational football

In keeping with studies on as well untrained men as on children (Krstrup et al. 2010a, Andersen et al. 2010; Bendiksen et al. 2012, Ørntoft et al. 2016), the training consists of different football exercises such as passes, shots, dribbling etc., and as small-sided games. The small-sided games are performed as ex. 3v3 on small goals (2x5 m goals).

The risk of injury is markedly higher in football matches (5 times higher) than during football training for young players (Brito et al. 2012). Nevertheless, it is emphasized, that muscle strains and twist injuries in joints also can occur during training on small goals. But the injury frequency for 10 year-old children in football training is approx. 5 per 1000 training sessions, and therefore low (Malina et al. 2006). Furthermore, the FIFA 11 for Health pilot study, including Danish 10-11 year-old school children, did not report any injuries during the training (Ørntoft et al. 2016).

### Tests and measurements

The participants will be tested in the start and end of their 10-week residential stay at the DCSH.

Furthermore, there are follow-up tests 3 and 12 months after their stay. The, in total, four tests days include measurements of physical fitness, physical performance, cognitive functions and questionnaires about health-knowledge, well-being and sleep patterns. For further descriptions, see below. Each test day is of approx. 4-5 hours duration.

## **Measurements**

Each test day is planned in collaboration with DCSH staff or parents (the fourth test day) and are performed by a member of the scientific group (Human physiologists).

*Anthropometric measurements:* Body weight and standing and sitting height are measured with a portable weight (Inbody 720) and altimeter, respectively. Moreover, the Inbody 720 will make an estimate of muscle mass and fat percentage. After a minimum of 10 min. of rest in the supine position in a quiet room, measurements of resting heart rate and blood pressure are performed.

*Balance and muscle strengths/vertical jumping length:* Balance performance is measured by the Stork test (Panta et al. 2015). It is measured on both legs, and best out of three trials counts as the result. The children stand barefooted or in one's stocking feet on the floor. With eyes open and their weight on the entire sole of the supporting foot, arms on the hips, and the not weight-bearing foot are placed on the inside of the opposite knee. When the child has found his/her balance, the heel of the supporting foot is lifted, and the timer starts. Time stops for following reasons:

- Hands/arms leave the hips.
- The supporting foot moves.
- The heel touches the floor.
- The foot, which rests on the knee, is removed from the knee.

Explosive leg strength is measured by standing longitudinal jumping, performed at two-legged offset and landing with arms placed on the hip in the starting position. The start position is behind a line on the floor and landing on a thin mat where the participants are instructed to land on their legs. Distances from the two-legged offset to the point where the rear heel affects the mat, is noted - best

out of 2 trials (Ortega et al. 2008, Reiman & Manske 2009). Standing longitudinal jump is correlated with both upper and lower body strength tests for children and adolescents and can therefore be considered as a general index for muscular fitness (Castro-Pinero et al., 2010).

*Aerobic fitness and intermittent performance:* The original Andersen interval run test is used for indirect estimation of maximal oxygen uptake (Andersen et al., 2008). The participants run back and forth between cones on a 20m lane and touch the line between the cones at each end. After 15 sec. the participants stops as soon as possible (about two steps) and rests for 15 seconds. This procedure is followed for a total of 10 minutes. The 15 sec. periods are indicated by music that stops during rest periods. All participants start and stop the test at the same time. The distance traveled is recorded as test result. This test has previously been performed in 6-13 year olds, and no risks or adverse effects have been observed relating to the testing performed. The test is also validated for children in the age group 6-13 years (Andersen et al., 2008, Ahler et al., 2012).

*Cognitive functions:* During the four test rounds, the participants are tested in a computer-based objective cognitive test battery that has been validated and verified in the age group 10-18 years to address children's cognitive functions (Cromer et al., 2015). The battery consists of four tests, which tests reaction time, attention, visual learning and long-term memory, work memory and executive functions (Cromer et al., 2015) - see further description below.

The reaction time is addressed by a 'Detection Test' (Houx and Jolles, 1993). The participant sits with the dominant hand's index finger resting on a yes button on the keyboard. On the screen there is a set of playing cards in a pile facing upside down. When the test starts, the first card turns so that the image page appears. As soon as this happens, the participant must press the yes button. Then the card disappears into the deck and a new card is turned, to which the participant must press the yes button again. The participant will be encouraged to work as fast and as accurately as possible. Response time for correct answers in milliseconds (lower response time = better performance) is the primary outcome that is stored and used in the following analysis.

The participants attention is measured using an 'Identification Test'. The participant has the right and left index fingers respectively resting on one yes and one no button. On the screen there is a set of

playing cards in a pile facing upside down. The test is initiated and a playing card is turned and is either red or black. The participant must now answer whether the card is red or not by pressing either yes or no button in accordance with the required response. Then the card disappears into the deck and a new card is turned. Response time for correct answers and number of errors are the primary outcome.

Participants 'visual learning are evaluated through a 'One Card Learning Test'. At 'One Card Learning Test ', the participant is sitting with the right and left index fingers respectively resting on one yes and one no button. On the screen there is a set of playing cards in a pile facing upside down. The test is initiated by turning the first card face up. The participant must now indicate whether the card has been shown before in the test by either pressing the yes or no button. Then the card disappears into the deck and a new card is turned. The participant must try to remember all cards shown in the test. The proportion of correct answers and response time are the primary outcome.

The participants 'working memory is addressed through a 'One Back Test'. The participant has the right and left index fingers respectively resting on one yes and one no button. On the screen there is a set of playing cards in a pile facing upside down. The test is initiated by turning the first card face up. The participant must decide whether the card is identical to the previously displayed card by pressing either the yes or no button. Then the card disappears into the deck and a new card is turned. Response time for correct response and the number of errors are the primary outcome.

The testing is done individually in a room by a laptop or desktop computer with internet access. Data collection takes place by participants having a unique username and login, which is entered using a sent link from the investigators. The tests last a maximum of 45 minutes in total.

*Metabolic markers:* Saliva Tissues collected by a Salivette tube are used to indicate the level of hormone insulin. The insulin level may indicate an increased risk of insulin resistance and type 2 diabetes (Goodson et al., 2014). Spit samples are kept as cold as possible until they can be centrifuged. Samples are centrifuged, supernatant stripped into cryo tubes, stored at -20 degrees, later -80 degrees. Hair samples for the determination of long-term exposure to the biomarker Cortisol, consisting of approx. 100 hairs cut as close to the scalp as possible. It is kept in an envelope until analysis (Suavé et al., 2007).

